9.2. Screening and eligibility assessment

9.2.1. Initial screening

Once parents/guardians or participants express an interest in joining the trial, they will be directed to a 2-part online screening process. The first part will assess for obvious exclusion criteria. If they pass this part, they will be asked to indicate their electronic consent to cover:

- Reporting the potential participant's medical history, including any history of SARS-CoV-2 infection identified by antigen detection, PCR testing or detection of SARS-CoV2 spike or nucleocapsid antibodies in the absence of COVID-19 vaccination
- Telephone screening visits to review their medical history (if required). Requirement to be determined by review of responses to Part 2 of online questionnaire)
- Permission to contact the participant's GP for further clarification of past medical history and vaccine status, should this be clinically indicated

Once Part 1 and consent have been completed, they may progress to Part 2. Here they will be asked to give details of any medical comorbidities or medications.

Participants without a past medical history or drug history that requires further review may be invited directly to enrolment/vaccination visits.

9.2.2. Telephone screening visit(s)

Participants for whom further clarification of eligibility is required, may be invited for telephone screening visit(s), which would then be completed by member(s) of the clinical team, based on the assessment of the part 2 responses. This will be recorded in a screening CRF. This will reduce the amount of time participants have with the clinical team during their screening procedures, should they progress to Visit 1.

We may also contact the participant's general practitioner with the permission of the volunteer. GPs will be notified at the time of enrolment (vaccination) that the subject is taking part in the study.

Volunteers will be asked to contact the study team if there are significant changes to their health status between screening and their Visit 1.

9.2.3. Screening

The final eligibility screening will be performed at the first visit.

9.3. Informed consent

Participants aged 16 years or over will be self-consenting as per the National Institute of Health Research guidelines. However, with the participant's permission, parents/guardians will be provided with information about the study by the trial team and via information available on the trial website, and the study team will request a parent/guardian to be at the first visit. If a participant aged 16 years declines parental notification, this will necessitate contact with their

named GP to corroborate their medical history before they are enrolled. This is to safeguard vulnerable young adults.

Consent will be taken by clinical staff (registered doctor or nurse) with appropriate experience and training. Where interested participants have vulnerabilities that may impair their capacity to provide informed consent, additional input or support from the individual's parents/guardians will be sought. If there is ongoing doubt about an individual's ability to provide informed consent, then they will not be enrolled in the study.

Children/adolescents aged under 16 of years will require full parental written consent as well as signed assent from the participant themselves. Individually each participant (and their parent/guardian) will have the opportunity to question an appropriately trained and delegated researcher before signing the consent form. Participants who turn 16 years during the course of the study will be required to sign a full informed consent form at the visit occurring after their 16th birthday.

Prior to consent, the participant (and their parent/guardian) will be fully informed of all aspects of the trial, the potential risks and their obligations. The following general principles will be emphasised:

A written version and verbal explanation of the Participant Information Sheet and Informed Consent will be presented to the participant of the participant detailing:

- The exact nature of the study
- What it will involve for the participant
- The implications and constraints of the protocol
- The known side effects and any risks involved in taking part
- The sample handling protocol – participants will be informed that anonymised samples taken during the study may be shared with study collaborators
- Individual results will not be shared with participants.
- The Participant Information Sheet will be made available to the participant for an appropriate amount of time (where possible this will be a minimum of 24 hours) prior to consent being obtained. A video presentation of the Participant Information Sheet may be screened to an audience, or made available for participants to access remotely. Participants will have the opportunity to individually question an appropriately trained and delegated researcher before signing consent.
- The following general principles will be emphasised:

- Participation in the study is entirely voluntary
- Refusal to participate involves no penalty or loss of medical benefits
- The participant may withdraw from the study at any time
- The participant is free to ask questions at any time to allow him or her to understand the purpose of the study and the procedures involved
- The participant will be informed that they will not know whether they have received an approved COVID-19 vaccine schedule. This may have implications for any travel or other activities that may require individuals to be considered 'fully immunised'.

Participants, like the general population, will not be exempt from following the contemporaneous government COVID-19 guidance to minimise viral transmission.

Samples taken as part of the study may be sent outside of the UK and Europe to laboratories in collaboration with the University of Oxford. These will be de-identified. Volunteers will be asked if they consent to indefinite storage of any leftover samples for use in other ethically approved research; this will be optional.

The participant will be allowed as much time as they wish to consider the information, and the opportunity to question the Investigator, their GP or other independent parties to decide whether they will participate in the study. Written informed consent will then be obtained by means of the participant/parent/guardian dated signature, and dated signature of the person who presented and obtained the informed consent. The person obtaining the consent must be suitably qualified and experienced, and be authorised to do so by the Chief/Principal Investigator and listed on the delegation log. A copy of the signed informed consent will be given to the participant/parent/legal guardian. The original signed form will be retained at the research study site, in the CRF.

9.4. Randomisation

Computer generated randomisation list will be prepared by the study statistician. Participants will be randomised 1:1:1 to the three study groups. After 29th November 2021, participants will be randomised 1:1 to the two study groups.

Participants will be randomised using block randomisation. Random block sizes of 3 and 6 will be used before 29th November 2021, and random block sizes of 2 and 4 will be used after 29th November 2021. Randomisation will be performed at the time of the second dose, and stratified by study site and anti-nucleocapsid IgG status at baseline (where available).

9.5. Blinding and code-breaking

The study will be single-blind. Staff involved in study delivery will be aware of which vaccine the participant is receiving (arm allocation); the participant will remain blinded to their boost vaccine allocation up until the day 84 visit, at which point participants will be advised of their immunisation arm. Vaccines will be prepared out of sight of the participant and the blind will be maintained by applying a masking tape over the vaccine syringe. Laboratory staff will also be blinded to the vaccine schedule received.

If the clinical condition of a participant necessitates unblinding of the participant prior to the day 84 visit, this will be undertaken according to a trial specific working instruction and group allocation sent to the attending physician. This will be done if unblinding is thought to be relevant and likely to change clinical management.

In order not to disadvantage participants in a rapidly changing landscape of rules affecting national and international travel as well as event attendance, we will make every effort to liaise with appropriate parties to ensure participants' vaccination status is recorded in the most suitable manner.

As of the 11th June 2021, the Department of Health and Social Care has confirmed that for any future domestic certification of vaccination status, clinical trial participants will not be disadvantaged, and will be offered an "immunised" status regardless of the licencing status or vaccine schedule received. This status would be available to trial participants while blinded, and also after unblinding even if they have received an unlicensed vaccine schedule.

9.6. Visits

The study visits and procedures will be undertaken by one of the clinical trials team. The procedures to be included in each visit are documented in the schedule of attendances (Each visit is assigned a time-point and a window period, within which the visit will be conducted. If a participant cannot attend a visit, where possible, this will be re-arranged to an in-person visit within the time window. A telephone visit may be conducted instead of the in-person visit to ascertain as much relevant information as possible if the participant is unable to attend a visit in person because of quarantine or self-isolation restrictions and the participant will be out of window if the visit is postponed.

Participants may enrol in the study either before receiving a COVID-19 vaccine (study-prime) or after receiving a first dose of Pfizer-BioNTech vaccine in the community (community-prime). The details of the D0 and D56 visits will differ for these two scenarios, as described below.

9.6.1. Visits for participants receiving their first dose of COVID-19 vaccine in the study

9.6.1.1. D0: Final eligibility check, enrolment and vaccination visit

9.6.1.1.1. Informed consent

The participant will have informed consent taken as described in Section 9.3 , before proceeding to the final eligibility check component of D0 visit. A video presentation of the aims of the study and all tests to be carried out may be screened to an audience or accessed remotely before informed consent is taken. This will be pitched at a level which should generally be comprehensible to the youngest participants. Individually, each volunteer and parent/legal guardian (if applicable) will have the opportunity to question an appropriately trained and delegated researcher before signing the assent/consent form.

9.6.1.1.2. Final eligibility check D0

During the final eligibility check component of D0 visit:

If written consent is obtained, the procedures indicated in the schedule of attendances will be undertaken including:

- Confirmation of medical history, including SARS-CoV-2 infection
- Physical examination (if required, determined according to past medical history)
- Height and weight
- Observations (temperature, heart rate)
- Urine pregnancy test in females

The eligibility of the volunteer will be reviewed by a study doctor. Decisions to exclude the volunteer from enrolling in the trial or to withdraw a volunteer from the trial will be at the discretion of the Investigator.

As per Section 8.3.1 “Temporary exclusion criteria”: If a volunteer has an acute respiratory illness (moderate or severe illness with/without fever) or a fever (oral temperature > 37.8°C) at D0/D56 visit screening, or a history of proven COVID-19 infection first confirmed less than 4 weeks earlier, the volunteer will not be enrolled that day, but may be considered for enrolment if they recover in sufficient time.

9.6.1.1.3. Samples taken at D0

- Blood tests including:
 - COVID-19 immunogenicity bloods
 - Markers of cardiac stress
- Nasal fluid and saliva sample (both optional, and at selected sites only)

9.6.1.1.4. Vaccination at D0

Participants will be considered enrolled to the trial at the point of receipt of the first vaccine administered by the study team. All vaccines will be administered intramuscularly according to specific SOPs. The participant will stay in the trial site for observation for at least 15 minutes, in case of immediate adverse events. Participants will be issued with an NHS COVID-19 vaccination record card at the first immunisation with entry of “BNT162b2” and batch number. This will be updated at the second immunisation, but boost vaccine type or batch number will not be added as this would unblind participants; instead, “COVID-19 vaccine”, “Com-COV3 Trial” will be added. We will correspond with holders of the participant’s medical information records (e.g. GPs) to enable updating of these records.

9.6.1.1.5. eDiary

Participants/parents/guardians will be given an oral thermometer, tape measure and diary (electronic, but for those who are unable to use an electronic diary, a paper version will be made available), with instructions on use. All participants will be given the emergency 24-hour telephone number to contact the on-call study physician if needed. Participants/parents/guardians will be instructed on how to self-assess the severity of the solicited and unsolicited AEs they are entering in the diaries. There will also be space in the diary to self-document unsolicited AEs, and whether medication was taken to relieve the symptoms. It will also log any serious medical illnesses or hospital visits which may have occurred over the entire course of the study and any diagnosis of SARS-CoV-2 infection. Given the potential for physical exercise to raise troponin and NT-proBNP independently of myocardial inflammation, there will be a space in the diary to record episodes of strenuous physical activity (“defined as anything that makes you feel really out of breath”) in the period between the booster vaccine and the D70 visit. Participants/parents/guardians will be asked to report on solicited AEs for 7 days from prime and boost dose (and longer if symptoms persist at day 7, until resolution or stabilisation of symptoms) and unsolicited AEs for 28 days. The Diary will collect information on the timing and severity of the following solicited AEs:

Table 1 Solicited AEs collected on post vaccination diary cards

Com-COV3 Protocol

©Copyright: The University of Oxford

Local solicited AEs	Pain, Tenderness, Redness, Warmth, Itch, Swelling, Induration
Systemic solicited AEs	Fever, Feverishness, Chills, Joint pains, Muscle pains, Fatigue, Headache, Malaise, Nausea, Vomiting, Diarrhoea

Post-vaccination (7 and 28 day) diary information will be reviewed by a clinician daily, and participants may be telephoned to discuss further, should there be any clinical concerns.

The diary will contain an instruction to contact the trial team by telephone should any encounter be a hospitalisation, or if they have concerns about their health.

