6. OBJECTIVES AND OUTCOME MEASURES

	Objectives	Outcome Measures	Timepoint(s)
Primary	To evaluate the reactogenicity of heterologous boost at least 8 weeks following BNT162B2 prime vaccine administered to adolescents.	Solicited reactions systemic	7 days after boost immunisation
Secondary	To assess safety of heterologous boost COVID-19 vaccines	Serious adverse events Adverse events of special interest	Throughout the study
	To characterise immunogenicity of heterologous & homologous boost schedules	Anti-spike immunoglobulins	D0*, 56, post prime D 14, 28, 132, 236 post boost
		Anti-nucleocapsid immunoglobulins	D0*, 56 post prime D132, 236 post boost
		Cellular immune responses by ELISpot	D0*, 56 post prime

			D 14, 132, 236 post boost
	To assess reactogenicity and safety of heterologous and homologous boost schedules of COVID-19 vaccines	Solicited local reactions	7 days after prime* and boost immunisation
		Unsolicited reactions	28 days after prime* and boost immunisation
	To evaluate immunogenicity, safety & reactogenicity of COVID-19 vaccines in participants seropositive for SARS-CoV-2 nucleocapsid IgG at enrolment, compared with seronegative	Immunogenicity, safety & reactogenicity endpoints as outlined above	Timepoints as outlined above
Exploratory	To assess incidence of SARS-CoV-2 infection in participants receiving heterologous & homologous prime/boost schedules	Self-reported SARS-CoV-2 infection, from community testing	Throughout the study
	To further characterise the blood antibody response	Neutralizing and Functional antibody assays	D0*, 56 post prime D 14, 28, 132, 236 post boost
	To characterise and compare the mucosal immune response to immunisation with homologous and heterologous COVID-19 vaccines using nasal fluid (collected using SAM-strips) and saliva samples	IgA & IgG ELISA and exploratory immunological assays	D0*, 56 post prime D14 post boost
	To determine normal ranges of markers of cardiac muscle damage in adolescents, and to assess change post-immunisation	High sensitivity troponin and N-terminal pro B-type natriuretic peptide (NT-proBNP)	D0*, 56 post prime D14, 28 post boost

* Only for participants receiving prime vaccination in the study

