12.4. Interim analyses

The analysis on the primary endpoint of reactogenicity, i.e. solicited AEs will be carried out once the 7-day e-diary data become available. The analysis on the secondary endpoint of immunogenicity will be carried out when the D70 immunogenicity data, i.e. 14 days post boost, become available. The interim analyses will provide evidence for policy making as to the recommendation on the second dose of COVID-19 vaccine among adolescents. The interim analyses will be carried out once the data is cleaned and the Study Analysis Plan is signed off. There will be no stopping rule for this interim analysis and the analysis will not affect the continuation of the trial.

After further discussion with Joint Committee on Vaccination and Immunisation (JCVI), the study team decided to carry out another interim analysis in December 2021. In this analysis, we will review the sero-status pre-boost as well as all the available immunogenicity data. These data will be shared with JCVI only to support decision making on boost dose among people aged 12-17. This interim analysis will be descriptive.

On 29th November 2021, the JCIV recommended that all 12 to 15 year-olds should be offered a second dose of BNT162b2 vaccine before reviewing the planned interim analysis in December 2021. The study design was amended to focus on immune response to full dose and one third dose of BNT162b2. The planned analysis in December will still be conducted and results will be

presented to JCVI to update their recommendation. The study's recruitment and sample size will then be reviewed on the basis of this analysis after discussing with JCIV, TSC and DSMB.

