25. APPENDIX C: BLOOD SAMPLING

Study timeline	D0	D56	D14 post boost	D28 post boost	D132 post boost	D236 post boost
COVID-19 vaccination	X	X				
Secondary endpoints	Anti-spike IgG* Anti-nucleocapsid IgG* ELIspot* Troponin & NT-proBNP*	Anti-spike IgG Anti-nucleocapsid IgG ELIspot Troponin & NT-proBNP	Anti-spike IgG ELIspot Troponin & NT-proBNP	Anti-spike IgG PBMC for storage Troponin & NT-proBNP	Anti-spike IgG Anti-nucleocapsid IgG ELIspot	Anti-spike IgG Anti-nucleocapsid IgG ELIspot
Total volume blood per visit	16	16	16	16	16	16
Total volume by end of study						96 ml

* Procedures performed only if prime dose administered in the study

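### Strenuous exercise is recorded only up to the day-14 post-boost visit, although troponin and NT-proBNP are also measured at day 28 post boost

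*Protocol*

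**What the plan says.** Section 9.6.1.1.5 (eDiary) gives the reason for collecting exercise data: "Given the potential for physical exercise to raise troponin and NT-proBNP independently of myocardial inflammation". The diary then has a space for strenuous activity "in the period between the booster vaccine and the D70 visit". Section 12.4 fixes what D70 means by referring to "the D70 immunogenicity data, i.e. 14 days post boost".

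The markers belong to an exploratory objective in Section 6: "To determine normal ranges of markers of cardiac muscle damage in adolescents, and to assess change post-immunisation". After the boost they are due at "D14, 28 post boost". Appendix A agrees, and the day-28 column of Appendix C reads "Anti-spike IgG PBMC for storage Troponin & NT-proBNP". Before the boost they are drawn at D56 for everyone and at D0 only in those primed in the study (Section 9.6.1.1.3; Appendix C footnote: "Procedures performed only if prime dose administered in the study").

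The amendment history (Appendix B) explains how the day-28 measurement arose: version 6.0 added it on DSMB advice, using blood already scheduled. The mismatch itself lies between current sections and does not depend on that log.

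**The concern.** The protocol has itself decided that these two markers need exercise information to be interpreted. It supplies that information for the first post-boost draw and not for the second. Avoiding myocarditis after a second full BNT162b2 dose is one of the stated reasons for the trial (Sections 2 and 5), so an isolated raised troponin at day 28 is a result that people will want to explain. On the data the protocol requires, exercise could be neither supported nor ruled out as the cause. The same holds for a participant's change from D56 to day 28.

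**Working it through.** The protocol states no figure on this point. The check sets the recording period against the draw schedule.

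**Inputs**
- Recording period: boost to the D70 visit (Section 9.6.1.1.5). 56 + 14 = 70, so this is the day-14 post-boost visit, as Section 12.4 confirms.
- Day-14 visit window: days 12 to 17 post boost (Appendix A).
- Day-28 visit window: days 28 to 42 post boost (Appendix A).
- E-diary adverse event entries: at most 28 days after each dose (Section 13.2).
- Community-primed participants receive their diary at the D56 visit (Section 9.6.2).

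**Marker draws and exercise record**

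| Draw | Who | Exercise recorded beforehand? |
|---|---|---|
| D0 | Study-primed only | No |
| D56 | All | No; recording opens at the boost |
| Day 14 post boost | All | Yes |
| Day 28 post boost | All | No; recording closed at the day-14 visit |

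The record therefore precedes 1 of 4 draws in study-primed participants and 1 of 3 in community-primed participants.

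**Unrecorded time before the day-28 draw** = day of the day-28 draw − day of the day-14 visit
- Shortest: 28 − 17 = 11 days
- Nominal: 28 − 14 = 14 days
- Longest: 42 − 12 = 30 days

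Even in the shortest case the last 11 days before sampling are missing.

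**Would a diary extension be enough?** If the exercise field ran to diary day 28, a draw on day 42 would still have 42 − 28 = 14 unrecorded days. Draws on days 29 to 42 would be covered only in part.

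**The case against.** Four points can fairly be made on the other side.

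- **Between-arm comparisons are protected.** Allocation is randomised at the boost, so exercise habits are balanced in expectation. Participants are to stay blinded until the day 84 visit (56 + 28 = 84, the day-28 visit), so knowledge of the arm should not change behaviour before that draw. This stands. A reader might infer that the arm contrast at day 28 is confounded by exercise, and the documents do not support that.
- **The absence of an exercise record before D0 and D56 contradicts nothing.** The diary item was tied to a post-boost sample, and whether a normal range should include adolescents who have recently exercised is a matter of definition that the protocol leaves open. This also stands: only day 28 is an internal mismatch.
- **No distorted reference limit can be shown.** It is tempting to argue that unrecognised post-exercise values at D0 and D56 would push up an upper limit and hide later rises. The protocol specifies no percentile limit. It gives no proportion of participants who exercise before a draw, and neither the size nor the duration of an exercise-related rise. Change after immunisation can also be assessed without a reference limit.
- **Sites can ask.** Interim medical history is taken at each of these visits (Appendix A), so a site could enquire when a value is raised. The protocol does not require this, and asking only after a raised value would give selective data. This softens the point without removing it.

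**Conclusion.** The point holds for day 28 post boost. The exercise record stops at the day-14 visit, the current schedule measures both markers again at day 28, and the 11 to 30 days before that draw (nominally 14) go unrecorded. The result rests on the protocol's own premise that exercise affects the markers, and on its visit windows being followed.

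The loss is confined to interpreting individual day-28 values and within-person change to day 28, on an exploratory endpoint. The primary reactogenicity endpoint, the immunogenicity comparisons, the sample size and the randomised marker comparisons are unaffected. How many day-28 values exercise would alter cannot be estimated from the document. The D0 and D56 draws offer an inexpensive improvement and are not a fault in the plan. Overall this is a minor point, worth correcting because doing so costs almost nothing.

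**What to change.** Reconcile Section 9.6.1.1.5 with Section 6 and Appendices A and C.

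1. At the day-28 post-boost draw, ask one question on strenuous activity in the preceding days, using the diary's existing definition. The sponsor should fix the look-back period, since the document gives none. A question at the draw covers the whole window to day 42, which a diary field ending at day 28 would not.
2. As an optional addition, ask the same question at the D56 draw and, in study-primed participants, at the D0 draw. These are the pre-boost samples that would naturally serve as the reference for change and for normal ranges.
3. Show marker values and changes with and without recently exercised participants, as a sensitivity presentation.
4. State as a limitation that exercise was not captured for visits already completed; this cannot be recovered.

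The cost is one short question per marker draw and slight participant burden. No extra blood, visit or participant is needed.

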7.3. Study groups

A total of up to 270 (+ up to an additional 10%) participants will be enrolled and randomised (1:1:1) as below:

Group	Arm	Prime (Day 0)	Boost (day 56)
	1	BNT162b2	BNT162b2
	2	BNT162b2	BNT162b2 (one-third dose)
	3	BNT 162b2	NVXCov2373

After 29th November 2021, the enrolment of participants who have received their first dose of COVID-19 vaccine in the community will be temporarily suspended. Only participants who have received their first dose of COVID-19 vaccine in the study will be randomised to a second dose. They will be randomised (1:1) as below:

Group	Arm	Prime (Day 0)	Boost (day 56)
	1	BNT162b2	BNT162b2
	2	BNT162b2	BNT162b2 (one-third dose)

Randomisation will be performed at the time of the second dose, and stratified by study site and anti-nucleocapsid IgG status at baseline where available.

The study will be single-blind, i.e. while staff involved in study delivery will be aware of what vaccine schedule the participant is receiving, the participant themselves will remain blinded to their boost vaccine. This blind will be maintained by applying a masking tape over the vaccine syringe as detailed in the study clinical study plan. Laboratory staff will also be blinded to the vaccine schedule received.

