12. STATISTICS

12.1. Sample size

The total sample size of this trial will be up to 270 Since the primary endpoint analysis will be descriptive and therefore no formal sample size calculation is carried out to determine the sample size of the trial. The number has been therefore chosen based on practical constraints. The precisions on estimating the systematic reactions based on 90 per arm are:

True event rate	Precision (normal approximation)	95% exact binomial CI
5%	±4.5%	1.5%-11.7%
10%	±6.2%	4.7%-18.1%
25%	±8.9%	16.5%-35.2%
50%	±10.3%	39.3%-60.7%

For secondary endpoints of immunogenicity, the minimum geometric mean ratios that can be detected with 90% power at two-sided 0.05 based on 90 per arm are:

Standard deviation on log10 scale	Minimum GMR to detect
0.4	1.57 (or 0.64)
0.5	1.75 (or 0.57)
0.6	1.96 (or 0.51)

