12.2. Description of statistical methods

A fully detailed statistical analysis plan will be developed and signed by the chief investigator prior to any data analysis being conducted. In brief, the analysis will incorporate the following:

Safety and reactogenicity

All SAEs will be presented for each group using descriptive analyses. Counts and percentages of each local and systemic solicited adverse reaction from diary cards, and all unsolicited AEs, and AEs of special interest will be presented for each group. Comparisons between the arms will be made using Fisher's exact test.

Immunogenicity

Highly skewed ELISA data will be log-transformed prior to analysis. The geometric mean concentration (GMC) and associated 95% confidence interval (CI) will be summarised by computing the anti-log of the mean of the log-transformed data.

The GMRs and CIs post boost will be calculated for each of the heterologous arms when comparing to the homologous arm.

Spike-specific T cell responses (ELISPOT) will be presented as geometric means and confidence intervals, or medians and interquartile ranges if non-normally distributed after log-transformation.

Comparisons of continuous immunogenicity data between different arms or at different time points will be made using a t-test if normal distribution can be rendered after log-transformation. Otherwise, Mann Whitney U test will be used.

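### Fisher's exact test cannot use the post-prime symptom diary, a pre-randomisation measure that study-primed participants already provide, so some precision in the between-arm reactogenicity comparison is left unused

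*Protocol*

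**What the plan says.** The primary outcome in section 6 is solicited systemic reactions in the "7 days after boost immunisation". Solicited local and unsolicited reactions are listed there after prime and boost, systemic ones after boost only. The diary itself covers both doses: "Participants/parents/guardians will be asked to report on solicited AEs for 7 days from prime and boost dose" (section 9.6.1.1.5), with one list of eleven systemic symptoms.

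Sections 7.3 and 9.4 place randomisation at the second dose. Before that, every study-primed participant has had the same full-dose prime. Community-primed participants receive an e-diary only at the D56 visit (section 9.6.2), so they have no post-prime record. From 29 November 2021 their enrolment is suspended, which section 7.3 calls temporary, and "Only participants who have received their first dose of COVID-19 vaccine in the study will be randomised to a second dose".

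For analysis, section 12.2 tabulates counts and percentages of each solicited reaction by group and adds "Comparisons between the arms will be made using Fisher"'s exact test. It describes its methods as a summary of a fuller statistical analysis plan, which was not available here. Section 12.1 states "Since the primary endpoint analysis will be descriptive and therefore no formal sample size calculation is carried out" and gives precisions for single-arm rates at 90 per arm.

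**The concern.** How strongly a person reacts to, and reports on, one dose may carry information about the next. A measure of the same symptoms, on the same instrument, taken before allocation, can be adjusted for without introducing bias, because the arm cannot have influenced it. In the 1:1 phase it is scheduled for everyone randomised, and that is the comparison to which the trial was redirected. A two-by-two exact test cannot use it.

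What is at stake is the width of the interval around the difference between full and one-third dose. Section 12.1 says that the sample size was set by practical constraints, so data already being collected are one of the few remaining sources of precision. Section 12.2 also names no between-arm effect estimate for reactogenicity, although it promises ratios with confidence intervals for immunogenicity.

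**Working it through.** **Inputs from the protocol.** 90 per arm and event rates of 5%, 10%, 25% and 50% (section 12.1).

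**Assumptions, because the protocol gives no figures.** Prime and boost severity follow a latent bivariate normal distribution with correlation 0.3, 0.5 or 0.6. The post-prime reaction rate is 0.8 times the post-boost rate. Post-prime severity is cut into grades 0-3, with half of reactors reaching grade 2 or more and 15% grade 3; using 40% and 10% instead changes the gains by no more than about 0.1 percentage points. The study-primed share f is 100% or 50%.

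**Step 1: the plan's own figures.** Single-arm half-width = 1.96 × √(p(1−p)/90). This gives 4.50, 6.20, 8.95 and 10.33 points, against the stated 4.5, 6.2, 8.9 and 10.3. The exact intervals also reproduce, for example 39.3%-60.7% at 50%. Adjustment does not alter these figures, because each describes one arm on its own.

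**Step 2: unadjusted between-arm half-width.** 1.96 × √(2p(1−p)/90):
- 50% in both arms: 1.96 × √(0.50/90) = 14.6 points
- 10%: 1.96 × √(0.18/90) = 8.8 points
- 5%: 1.96 × √(0.095/90) = 6.4 points

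**Step 3: with adjustment.** R² is the share of variance in the post-boost any-versus-none outcome explained by post-prime grade. The half-width is multiplied by √(1 − f·R²), and the gain in effective sample size is 1/(1 − f·R²) − 1. For example, at a 50% rate, correlation 0.5 and f = 100%, R² = 0.12. The gain is 1/0.88 − 1 = 14%, and the half-width is 14.61 × √0.88 = 13.7.

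| Event rate | Latent correlation | R² | Gain, f = 100% | Half-width, f = 100% | Gain, f = 50% |
|---|---|---|---|---|---|
| 50% | 0.3 | 0.042 | 4% | 14.6 → 14.3 | 2% |
| 50% | 0.5 | 0.120 | 14% | 14.6 → 13.7 | 6% |
| 50% | 0.6 | 0.177 | about 22% | 14.6 → 13.3 | 10% |
| 10% | 0.3 | 0.016 | 2% | 8.8 → 8.7 | 1% |
| 10% | 0.5 | 0.063 | 7% | 8.8 → 8.5 | 3% |
| 5% | 0.3 | 0.009 | 1% | 6.4 → 6.3 | 0.5% |
| 5% | 0.5 | 0.042 | 4% | 6.4 → 6.2 | 2% |

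**Step 4: simulation check.** 4,000 trials per scenario, 90 per arm, 50% versus 30%, using a linear-probability model with robust standard errors and an indicator for a missing prime diary. Correlation here is between the observed yes/no outcomes; a latent 0.5 at a 50% rate corresponds to about √0.12 = 0.35 observed. With everyone study-primed, the ratio of adjusted to unadjusted variance was 0.96, 0.92 and 0.84 at observed correlations of 0.2, 0.3 and 0.4, against 0.96, 0.91 and 0.84 from the formula. At zero correlation it was about 1.01, so an uninformative diary costs almost nothing.

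**Step 5: what not to credit to the covariate.** At zero correlation the adjusted test already had 79-80% power, against 75% for Fisher's test. Under the null (correlation 0.3), Fisher's test rejected 3.4% of the time and the adjusted test 4.8%. That gap of roughly 4 points reflects the conservatism of the exact test, not the diary.

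**The case against.** The strongest reply is that nothing is wrong. Fisher's test is valid, section 12.2 is a summary, and covariates are commonly settled in the analysis plan, which may already contain an adjusted analysis. This stands as far as error goes, and it keeps the point minor. It does not remove the point, because the one between-arm method that the protocol names cannot use the covariate.

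A second reply is that modelling each symptom would be fragile. At 5-10% there are about 4.5-9 events per arm, and several grade levels plus a level for missing diaries could produce empty cells or separation. This stands too, and it limits the proposal to a common composite.

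Three stronger readings are tempting, and the protocol does not support them:

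- A reader might infer that every participant has a post-prime diary. Community-primed participants have none, their share is not stated, and they could be randomised throughout the 1:1:1 phase, the only one in which the NVXCoV2373 arm was open.
- A reader might infer that a powered primary contrast is weakened. Section 12.1 calls the primary analysis descriptive and reports only single-arm precision. Its power statement concerns secondary immunogenicity.
- A reader might infer that the post-prime systemic data have no use. They are missing from the outcome table after prime, but section 12.2 tabulates diary reactions without restricting them to the boost, and section 9.6.1.1.5 has clinicians review the diaries daily. What is missing is a stated use in the between-arm comparison.

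**Conclusion.** The point holds as a modest efficiency gain. For study-primed participants the post-prime diary is a legitimate baseline for post-boost systemic reactions, and the stated test cannot use it. No bias, invalid test or wrong figure is involved.

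The size rests on a correlation that the protocol does not give. Under the assumed latent range of 0.3 to 0.5 the gain is worth having for outcomes near 50% in the 1:1 phase, and small for rare symptoms or a low correlation. The 22% in the table needs a correlation of 0.6, a common outcome and every participant study-primed together, so it should not be taken as the expected gain. Where half are study-primed, the gains at a 50% rate and correlation 0.3 to 0.5 fall to 2-6%.

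**What to change.** Keep the counts, percentages and Fisher's exact test as they are. Unless the statistical analysis plan already does so, pre-specify in addition one between-arm risk difference with 95% CI for a common composite of post-boost systemic reactions, such as any systemic reaction; a maximum-grade outcome could serve the same purpose. Adjust it for the participant's maximum post-prime systemic grade and for priming route, with a level marking the diary as not collected for community-primed participants. Leave rare individual symptoms to Fisher's test.

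The cost is a few lines in the analysis plan and one extra model. No new data, visits or participants are needed. The downside is little return if the correlation proves low. The composite and the grade categories must be fixed before the post-boost data are analysed by arm.
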